Evaluating the Value of Telehealth for Care of Children With Medical Complexity
Clinicaltrials.gov Identifier: NCT02849938
Unique Protocol ID: CCCMCTeleMed

Study Protocol and Statistical Analysis Plan

Last Revised: September 29, 2016

Participants

This study was designed as a single center, randomized, non-blinded pilot study. Sample size was determined by number of eligible patients enrolled in the Coordinated Care for Children with Medical Complexity (CCCMC) program at our institution as well as number of devices that were available for the pilot. Inclusion criteria included: patients aged 1 month to 18 years, currently enrolled in the CCCMC program; parent consent; at least one English-speaking parent; and in-home Wi-Fi connectivity. Children enrolled in the CCCMC program met the following criteria: 3 or more body systems requiring active management; technology dependent or full support to complete activities of daily living; and moderate or severe neuromotor delays, or intellectual disability. Children were excluded from this pilot study if caregivers expressed an inability to comply with study requirements. Participants were randomized 1.5:1 with stratification based on tracheostomy status to control group or intervention group (Research Randomizer, Urbaniak). This stratification was done to attempt to balance patient contact between the groups based on the assumption that patients with tracheostomies may require more frequent contact with the CCCMC team. Clinicians in the CCCMC program included a pediatrician and pediatric nurse practitioner. This study and subsequent revision was approved by the Advocate Health Care Institutional Review Board and registered at ClinicalTrials.gov (Identifier: NCT02849938).

Telehealth Device

The selected telehealth device (TytoHome™) is an FDA-approved, handheld, mobile device designed for capture and transmission of ear, throat, and skin images, heart and lung auscultations including heart rate detection, and temperature data taken by infrared transdermal thermometer. The device required pairing with an iOS tablet (Apple iPad mini 4) for transmission via wireless network for live-interactive clinician connection. Caregivers used the telehealth device to perform non-invasive medical examinations in the home for remote view by a clinician. TytoCare™ provided the telehealth devices and the iPad minis that were used in the pilot.

Procedure

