The impact of device utilization was evaluated by measuring the total number of visits per patient by type (outpatient visits of low, moderate, and high complexity; ED visit without subsequent admission, general pediatric ward days, pediatric intensive care unit days) as determined via chart review. To adjust for the difference in sample size per group, the number of hospitalization days, acute office visits, and ED visits were reported descriptively as a *visit rate* calculated as the number of visits or hospital days/patient study months (number of patients in the group x number of study months). Four months of data were used for the calculation because the control group did not have any

hospitalizations during the technical month. The Kaplan-Meier method was used to estimate the proportion of each group that did not have any hospitalizations during the study period. A statistical comparison of the survival distribution was not conducted because the Kaplan-Meier method does not account for repeated episodes such as patients with more than one hospitalization.

A negative binomial regression model with Generalized Estimating Equations to handle repeated measurements was used to test the difference in hospital length of stay between groups. Model results were reported as regression coefficients, 95% Wald confidence intervals and p values. The negative binomial regression model was appropriate for this analysis, as the distribution of the outcome had greater variability than expected under a Poisson distribution. The sample mean of the outcome (4.3) was substantially smaller than its variance (102.3). Regression models were not tested for the number of acute office or ED visits because the incidence rate was too small for the inferential statistic. Analyses were conducted using SPSS (version 22.0) (IBM Corp. Released 2013. IBM SPSS Statistics for Windows, Version 22.0. Armonk, NY: IBM Corp). For all analyses, a p value < 0.05 was considered statistically significant.

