Direct cost for each encounter was obtained from our institution's financial accounting system (EPSi), which was used to calculate direct costs per study group and encounter type (not including overhead costs such as cost of the telehealth device or connectivity). For the intervention group, a telemedicine visit was equated to a Level 4 return encounter in the outpatient setting. Direct cost savings were calculated as the absolute difference between the two study groups. To adjust for the difference in group sample size, the

encounter direct cost was multiplied by the visit rate and the adjusted cost rates were described for each group. Potential cost savings were calculated using clinician input on the visit types that were likely prevented as a result of the telemedicine device.

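### Direct cost savings are planned as a bare difference between groups, with no child-level spread or interval, so a reader cannot tell a saving from no difference or a loss

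*Combined protocol and SAP*

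**What the plan says.** The Analysis section takes direct cost for each encounter from the institution's accounting system, "which was used to calculate direct costs per study group and encounter type". It then defines the result: "Direct cost savings were calculated as the absolute difference between the two study groups". To allow for unequal group sizes, "encounter direct cost was multiplied by the visit rate and the adjusted cost rates were described for each group". The visit rate is defined earlier in the same section as group visits or hospital days over patient study months. It is pooled over the group and reported descriptively.

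No standard deviation, interval, test, resampling or sensitivity analysis is attached to cost. Hospital length of stay, by contrast, gets a negative binomial GEE model with 95% Wald intervals and p values. That choice is justified by overdispersion: "The sample mean of the outcome (4.3) was substantially smaller than its variance (102.3".

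**The concern.** The child is the randomised unit, so uncertainty in a between-arm cost difference comes from how cost varies between children. The plan builds the result from group totals and pooled rates and never brings that variation in. Followed exactly, it yields one number labelled savings, with nothing to show how far chance could have moved it.

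This matters because hospital days are likely to drive much of the cost, and the plan's own figures show that they are very uneven. The title presents the study as an evaluation of telehealth's value, so readers are likely to quote the cost figure. The plan quantifies uncertainty for length of stay but not for the cost result that depends on it.

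**Working it through.** The documents give no cost, cost difference or sample size, so there is no stated figure to reproduce. What follows is an illustration, with hospital days as a proxy for cost.

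**Inputs from the plan.** Mean 4.3 and variance 102.3 (Analysis); 1.5:1 allocation, read as control to intervention from the order of the sentence in Participants ("Participants were randomized 1.5:1 with stratification based on tracheostomy status to control group or intervention group"); four months of follow-up for the rates (Analysis).

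**Assumptions.** Arm sizes of 12:8, 24:16 and 60:40, because Participants gives only the basis for the sample size and no number. The unit of 4.3 and 102.3 is not stated, so two cases are shown.

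**Spread.** SD = √102.3 = 10.11. Variance/mean = 102.3/4.3 = 23.8. Negative binomial dispersion k = (102.3 − 4.3)/4.3² = 5.30.

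**Case A: the unit is the child.** Half-width = 1.96 × 10.11 × √(1/n_c + 1/n_i).
- 12:8: 1.96 × 10.11 × 0.4564 = 9.05 days; 9.05/4.3 = 210%
- 24:16: 1.96 × 10.11 × 0.3227 = 6.40 days; 149%
- 60:40: 1.96 × 10.11 × 0.2041 = 4.05 days; 94%

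**Case B: the unit is the child-month, with independent months.** The four-month mean is 4 × 4.3 = 17.2 and the variance is 4 × 102.3 = 409.2 (SD 20.23).
- 12:8: 1.96 × 20.23 × 0.4564 = 18.10 days; 18.10/17.2 = 105%
- 24:16: 12.80 days; 74%
- 60:40: 8.09 days; 47%

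Correlation between a child's months widens Case B. At an assumed correlation of 0.5 the variance is multiplied by 1 + 3 × 0.5 = 2.5, and the half-widths become 166%, 118% and 74% of the mean.

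**Apparent savings with no true effect.** Both arms were simulated from the same negative binomial distribution (mean 4.3, k = 5.30; four independent draws per child in Case B). The table gives the chance that the intervention arm's mean is at least 30% below the control arm's.

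| Control:intervention | Case A | Case B |
|---|---|---|
| 12:8 | 41% | 27% |
| 24:16 | 35% | 19% |
| 60:40 | 24% | 7% |

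The results depend strongly on the unit and the arm sizes. If the unit is the single hospital stay, neither case applies.

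**The case against.** This is a declared pilot, its cost analysis is descriptive, and a descriptive cost estimate is acceptable. The reader also sees uncertainty on length of stay through the GEE model. Both points stand, but an interval is itself a description, and the length-of-stay interval is not carried into cost. The general rule for continuous variables (means and SDs, then a t-test or Mann-Whitney test) does not name cost, and cost as defined has no child-level values to which it could apply.

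Several stronger readings are tempting, and the documents do not support them:

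- **That no standard error could be formed.** Cost is obtained for each encounter and visits are counted per patient, so child-level cost can be assembled. It is simply not planned.
- **That there is no per-patient cost at all.** The adjusted cost rate is an average per patient-month. What is missing is its spread.
- **That the difference is mostly noise, or driven by one or two long stays.** This needs the arm sizes and the unit of 4.3 and 102.3. Using GEE for repeated measurements makes the child-month a plausible unit, and that roughly halves the relative half-widths if months are independent.
- **That chance will be reported as a saving.** On rates, with no true effect, chance favours the intervention only about half the time (50–53% in the simulations).
- **That savings are taken on unadjusted totals.** The savings sentence comes before the size adjustment, so a reader might infer this. If so, and if control is the larger arm, equal cost per child would still give an expected gap of (1.5 − 1)/1.5 = 33% of the control total. The text does not settle which quantity is subtracted.
- **That cost is the leading outcome.** The title suggests value, but outcome measures are referred to Table 1, which is not in the text available here.

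**Conclusion.** The point holds: the planned cost result is a point difference with no child-level spread or interval, so its compatibility with zero or with the opposite sign cannot be judged. This follows from the text and needs no assumption.

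Its size is illustrative. Over the assumed arm sizes, the 95% half-width runs from 94% to 210% of the mean with the child as unit, and from 47% to 105% with independent child-months. The corresponding chances of a spurious reduction of 30% or more are 24–41% and 7–27%. These figures rest on assumed arm sizes, an assumed unit, a negative binomial shape for the simulated chances, and days standing in for cost. They show that the missing interval could be wide. They do not estimate the trial's actual precision.

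**What to change.** Replace the bare difference of group totals with a child-level analysis:

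- Sum each child's direct cost over all encounters, including telehealth visits at the plan's own assigned cost, and divide by that child's study months.
- Report arm means, SDs and the difference (intervention minus control) with a 95% interval that uses the child as the unit. Welch would serve, as would a bootstrap suited to small, skewed samples; having an interval matters more than which one.
- Add a sensitivity result without the costliest child.
- Describe the result as an exploratory estimated cost difference.
- State the arm sizes and the unit of the 4.3 and 102.3 figures, so that readers can judge the precision.

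The encounter costs are already obtained, so this takes SAP wording and a little analysis work, with no change to trial conduct. The downside for the sponsor is that any stated saving will look less certain. This is a cheap improvement.

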The length of the study observation period was increased from 3 to 4 months due to technology issues that were encountered and managed during the first month of the study (termed “technical month”). Data collection included subject demographics, encounter details (outpatient clinic visits, ED visits, and hospitalizations) that were routinely collected as a part of the CCCMC program, as well as caregiver and clinician surveys, which used a 4-point Likert response scale. All caregivers answered questions about CCCMC program satisfaction, and those in the intervention group answered additional questions about their comfort using the device. Caregivers were emailed a link to the online survey once a month during the study period. Surveys not completed online were conducted over the phone by a member of the study team who did not participate in patient care. Clinicians completed an online survey for each encounter in which they would have liked to complete a telemedicine visit regardless of child’s group assignment. They answered general satisfaction questions as well as demographic, feasibility, and

usability questions. Questions on the feasibility and usability of the telehealth device addressed the success of device connectivity, as well as the transmission of real-time images, temperature, and sound. Other questions asked about potential or actual changes in patient management because of the telehealth device. Specific measures to address each study outcome can be found in Table 1.

Analysis

Descriptive statistics were used to summarize data with absolute and relative frequencies for categorical variables and means and standard deviations (SD) for continuous variables. Feasibility and usability of the device as determined from survey responses and reported as median and interquartile range (IQR). Continuous variables were examined using independent groups Student's t-test or the Mann-Whitney U test depending upon normality of data. Dichotomous variables were examined using Chi-square or Fisher exact tests. Data are reported for the first technical month and subsequent 3-month observation period separately.

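### Potential cost savings counts only visits that unblinded clinicians judge prevented, with no stated deduction for telemedicine visits or added care and no check against control-arm rates

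*Combined protocol and SAP*

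**What the plan says.** The cost part of the Analysis section describes two quantities that are both called savings.

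- The first compares the randomised groups: "Direct cost savings were calculated as the absolute difference between the two study groups". To allow for unequal group sizes, the "encounter direct cost was multiplied by the visit rate and the adjusted cost rates were described for each group".
- The second rests on opinion: "Potential cost savings were calculated using clinician input on the visit types that were likely prevented as a result of the telemedicine device". This sentence is the whole rule. No formula, uncertainty measure or comparator is given.

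The same part prices a telemedicine visit as a Level 4 return outpatient encounter. It does not say whether that price is deducted from the second quantity.

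Other sections bear on how the clinicians' judgement arises. Participants states: "This study was designed as a single center, randomized, non-blinded pilot study", and adds: "Clinicians in the CCCMC program included a pediatrician and pediatric nurse practitioner". Data Collection states: "Clinicians completed an online survey for each encounter in which they would have liked to complete a telemedicine visit", in either arm, and describes the survey content: "Other questions asked about potential or actual changes in patient management because of the telehealth device". Procedure allows telehealth visits booked ahead for routine care or for practice with the device. It also says that clinicians in both arms may direct a family to the ED, the clinic or the hospital.

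**The concern.** A saving is a difference between what happened and what would have happened otherwise. This rule, as worded, records one side of that difference: visits that a clinician believes did not take place. Three things that could lower the figure are not mentioned: the cost of the telemedicine visit itself, any care that followed only because of the telehealth examination, and the rate of the same visits among control patients.

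The people who appear to supply the judgement treat the patients and know the allocation. If they overcall prevention, nothing in the rule pulls the figure back.

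A reader could therefore be shown a positive saving from a device that changes nothing, next to a randomised comparison that shows no saving. Nothing in the plan says which of the two should be believed, or that they should not be added together.

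**Working it through.** The plan states no amount for potential savings, no unit costs, no visit counts and no sample size, so there is no figure to reproduce. The check is of the rule's sign and of how it behaves when the device has no effect.

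**Step 1. Gross reading (only what is stated).** Let n_k be the number of visits of type k judged prevented and c_k the direct cost of one.

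S_gross = Σ n_k × c_k

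Both factors are zero or more, so S_gross ≥ 0. It equals zero only if no visit with a positive cost is judged prevented.

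**Step 2. Net reading (every telemedicine visit charged).** Let p be the share of telemedicine visits judged to have prevented another visit, and r the cost of the prevented visit divided by the cost of a telemedicine visit. In units of one telemedicine-visit cost, per telemedicine visit:

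S_gross = p × r, and S_net = p × r − 1

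S_net is negative whenever p < 1/r.

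| r (assumed) | Break-even p = 1/r | p = 0.10: gross / net | p = 0.25: gross / net |
|---|---|---|---|
| 1 | 1.00 | 0.10 / −0.90 | 0.25 / −0.75 |
| 2 | 0.50 | 0.20 / −0.80 | 0.50 / −0.50 |
| 5 | 0.20 | 0.50 / −0.50 | 1.25 / 0.25 |
| 10 | 0.10 | 1.00 / 0.00 | 2.50 / 1.50 |

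At r = 5 and p = 0.10 the same data give a gain of 0.50 or a loss of 0.50 telemedicine-visit costs per visit, depending only on a choice that the plan does not state.

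**Step 3. A case fixed by the plan's own pricing.** If the visit judged prevented is itself a Level 4 return encounter, r = 1. One telemedicine visit replacing one such visit saves 1 − 1 = 0. The gross rule credits one full Level 4 cost.

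**Step 4. Which visits are charged.** If only the telemedicine visits judged preventive are charged, S = p × (r − 1), which is again never negative when r ≥ 1. Scheduled routine and practice visits would then carry no cost in the figure. The formula must therefore say which visits are charged, as well as whether any are.

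**Step 5. Behaviour under no effect (illustration; every input assumed).** Take 24 control and 16 intervention patients, which matches the ratio in "Participants were randomized 1.5:1 with stratification based on tracheostomy status to control group or intervention group" read in the order written. Assume 4 months, 0.1 visits per patient-month in both arms, 30 telemedicine visits, unit cost 1, and a device that prevents nothing. If clinicians wrongly label 5%, 10% or 25% of telemedicine visits as preventive, the expected gross saving is:

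- 30 × 0.05 = 1.5 visit-costs
- 30 × 0.10 = 3.0 visit-costs
- 30 × 0.25 = 7.5 visit-costs

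In 100,000 simulated trials at each rate, the gross figure was negative in 0%. The signed between-arm difference averaged about 0 and was negative in about 47%. The comparison shows the kind of bias, not its size in this trial.

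**The case against.** The strongest reply is that no formula is given, so a reader cannot assert that the telemedicine cost was left out. The plan prices that visit in the same part of the text, so a deduction was possible. This stands. That the figure can never be negative is a tempting inference, but it holds only on the gross reading. The supportable statement is that no deduction is stated and that the answer depends on it.

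Four other inferences go further than the documents allow.

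- *The cost analysis ignores the control arm.* It does not. A between-arm difference and cost rates by group are both planned. Only the clinician-based figure lacks that comparison, and it carries its own label, potential.
- *The two savings figures are double counted.* Nothing says that they are added. How far they overlap also depends on whether control-arm survey responses enter, which is not stated.
- *The rule yields a saving even if nothing is prevented.* It does so only if some visit is mistakenly judged prevented. If none is, the gross sum is zero. Unblinded judgement makes such errors plausible but does not make them certain.
- *Only surveyed encounters count.* The cost text does not name the survey as the source of the clinician input. Table 1, which Data Collection cites for the outcome measures, is not in the text available here, so some of this detail may exist.

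Two cautions also apply to the remedy. Referral after assessment occurs in both arms, so a referral that follows a telehealth examination is not automatically added care. The survey items are not shown, so whether they recorded escalation is unknown.

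None of this supplies a formula, an offset or a benchmark for the figure.

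**Conclusion.** The point holds for one figure. As worded, potential cost savings has a single input, visits that unblinded clinicians judge to have been prevented. Read that way it has a floor at zero and is biased upward whenever a visit is wrongly attributed to the device. Charging the telemedicine visits removes the floor and can change the sign.

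No size can be given for this trial, because the documents contain neither the costs nor the counts. The break-even shares follow from algebra for assumed cost ratios of 1 to 10, and the no-effect results rest wholly on assumed inputs. The result for a replaced Level 4 return visit (net zero, gross one full visit cost) needs no assumption beyond the plan's own pricing.

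The randomised cost comparison is not affected. This should be corrected, but it does not invalidate the cost analysis as a whole.

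**What to change.** 1. Reserve the name cost savings for the signed between-arm difference in direct cost per patient-month. The adjusted cost rates by group already provide it by subtraction. Confirm that the word absolute in the plan means a difference in cost units and not a difference stripped of its sign.
2. Keep the clinician-based figure as supplementary and exploratory, and write out its formula: cost of visits judged prevented, minus the cost of telemedicine visits, minus the cost of visits judged added, where the survey or chart review recorded them. Say which telemedicine visits are charged, and show scheduled routine and practice visits on their own line.
3. State the source of the clinician input and which arm's encounters enter.
4. State that this figure is not added to the between-arm difference.
5. For each visit type, print claimed prevented visits per patient-month beside the observed between-arm difference in visit rate.

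The cost is some plan wording and a modest re-analysis. The Level 4 price, the chart-review encounters and the group rates are already part of the plan. The term for added visits depends on what was recorded; if nothing was, say so and report the figure as incomplete. The downside is that the potential-savings figure becomes smaller and may turn negative.
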